By identifying biologic treatment options, the proposed study will trigger a line of research to shift the treatment paradigm away from isolated surgical treatment of the ACL meniscus to a model in which both the joint and the modifiable postoperative pro-inflammatory state are treated to slow the progression of PTOA and prevent its associated sequelae. We will recruit a sample of 30 skeletally mature patients between the ages of 18 and 40 that have undergone ACL reconstruction with concomitant traumatic meniscus tears. At the time of surgery, patients will be screened for persistent inflammation by assessing synovial fluid IL-1alpha at that time. Those with elevated IL-1alpha will then be randomized to either extended-release triamcinolone acetonide or placebo (saline) 8 weeks after surgery. To assess the efficacy of extended-release triamcinolone acetonide, the following data will be collected at 8 week and 6 month follow-ups: 3T MRI, urinary and serum biomarkers of cartilage degradation, and patient-reported outcomes.

Objectives

List your research objectives. Please include a summary of intended research objectives in the box below.

Primary Objective: Determine if extended-release triamcinolone acetonide treatment alters the progressive changes in bone shape previously demonstrate after anterior cruciate ligament (ACL) reconstruction with partial meniscectomy or meniscal repair.

Secondary Objectives: Compare the change in patient-reported outcomes and a urinary biomarker of cartilage breakdown (uCTXII) between patients treated with extended release triamcinolone acetonide or placebo following ACL reconstruction with partial meniscectomy or meniscal repair.

Study Design

Describe and explain the study design (e.g., observational, secondary analysis, single/double blind, parallel, crossover, deception, etc.).

- *Clinical Research*: Indicate whether subjects will be randomized and whether subjects will receive any placebo.
- *Community-Based Participatory Research*: If you are conducting [community-based participatory research \(CBPR\)](#), describe strategies for involvement of community members in the design and implementation of the study, and dissemination of results from the study.
- *Qualitative research*: Indicate ranges where flexibility is needed, if a fixed interview transcript is not available, describe interview topics including the most sensitive potential questions.

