- *Research Repositories*: If the purpose of this submission is to establish a Research Repository (bank, registry) and the material you plan to collect is already available from a commercial supplier, clinical lab, or established IRB approved research repository, provide scientific justification for establishing an additional repository collecting duplicate material. Describe the repository design and operating procedures. For relevant information to include, see the [UK Research Biospecimen Bank Guidance](#) or the [UK Research Registry Guidance](#).

We will perform a Phase 2a, double-blind, placebo-controlled, randomized controlled trial to determine if a long-acting anti-inflammatory agent (extended-release triamcinolone acetonide) lessens progressive changes in bony shape, improves patient-reported outcomes, and/or reduces biomarkers of cartilage degradation when compared to placebo (saline). The single-site study is driven by the three guiding hypotheses:

Hypothesis 1: The shape changes of the femoral condyle between 8 weeks and 6 months after surgery will be significantly lower for patients treated with extended-release triamcinolone acetonide than the placebo group.

Hypothesis 2: Changes in patient reported-outcomes between eight and 6 months after surgery will be significantly greater for those treated with long-duration anti-inflammatory injections than the placebo group.

Hypothesis 3: Changes in a urinary biomarker of cartilage breakdown (uCTXII) between eight and 6 months after surgery will be significantly lower for those treated with long-duration anti-inflammatory injections than the placebo group.

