Determine if extended-release triamcinolone acetonide treatment alters progressive changes in bone shape after ACL reconstruction. The bone area of the medial femoral condyl has been shown to increase within the first few months after ACL reconstruction. This is clinically meaningful as similiary bony changes have been previously associated with progressive OA and within 6 months of ACL reconstruction correlated with subsequent patient-reported outcomes and MRI markers of cartilage quality at 3 years. All subjects will undergo MRI examination prior to undergoing the study injection at Visit 3 and again at Visit 4. Sagittal and axial MRI images will be acquired with the knee in full extension using a 3.0-T MRI scanner and an 1Tx/15Rx phased array knee coil. Sagittal and axial T1-weighted spin echo images (FSE) will be acquired to allow semi-quantitative analysis at the conclusion of the study. These sequences will be followed by a sagittal high-resolution 3D dual echo steady state (DESS) sequence for cartilage segmentation and a sagittal combined T1/T2 mapping for the quantification of cartilage composition.

Bone volume of the medial femoral condyle will be measured using previously validated methods. A single investigator experienced with quantitative and semi-quantitative assessments of knee MRIs⁴¹, will manually segment the medial femoral condyle on each slice of the MRI. Since the thickness of each slice is 3.5 mm, we will then calculate the medial condyle volume on each slice and then sum the volumes of all slices to generate the total medial condyle volume.

SECONDARY OBJECTIVES

Compare the change in patient-reported outcomes between patients treated with extended release triamcinolone acetonide or placebo following ACL reconstruction. The change in patient-reported outcomes (IKDC score, KOOSglobal score, and the Intermittent and Constant Osteoarthritis Pain (ICOAP) score) between the date of injection and the 6-month, 1-year, and 2-year postoperative follow-ups. The IKDC and KOOSglobal are knee-related patient-reported outcome tools. The IKDC has been validated in this specific patient population, and we developed and validated the KOOSglobal for use with young and potentially more active patient populations. The ICOAP was developed as part of the OARSI/OMERACT initiative and is a valid and reliable tool to assess OA-related pain.

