Does your research fall under the purview of any of the other review committees listed below? *[If yes, check all that apply and attach applicable materials using the attachment button at the bottom of your screen.]*

Yes No

Additional Information

- Institutional Biosafety Committee
- Radiation Safety Committee
- Radioactive Drug Research Committee
- Markey Cancer Center (MCC) Protocol Review and Monitoring Committee (PRMC)
- Graduate Medical Education Committee (GME)
- Office of Medical Education (OME)

- [Institutional Biosafety Committee \(IBC\)](#) - Attach required IBC materials
- [Radiation Safety Committee \(RSC\)](#) - For applicability, see instructions and attach form
- [Radioactive Drug Research Committee \(RDRC\)](#)
- [Markey Cancer Center \(MCC\) Protocol Review and Monitoring Committee \(PRMC\)**](#) - Attach MCC PRMC materials, if any, per instructions.
- [Office of Medical Education \(OME\)](#)
- [Graduate Medical Education Committee \(GME\)](#)

Attachments

**** If your study involves cancer research, be sure to select "Cancer Research" in the "Research Attributes" section.** ORI will send your research protocol to the Markey Cancer Center (MCC) Protocol Review and Monitoring Committee (PRMC). The [MCC PRMC](#) is responsible for determining whether the study meets the National Cancer Institute (NCI) definition of a clinical trial and for issuing documentation to you (the investigator) which confirms either that PRMC approval has been obtained or that PRMC review is not required. Your IRB application will be processed and reviewed independently from the PRMC review.

53136 Statistical Analysis Plan:

Primary objective will be assessed using two-tailed independent t-tests for comparison between timepoints. Similarly, all secondary measures will be assessed using two-tailed independent t-tests.

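### The SAP's only sentence on the primary analysis compares timepoints, not arms, so as written it does not test Hypothesis 1

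*Combined protocol and SAP*

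**What the plan says.** The section headed 53136 Statistical Analysis Plan has two sentences. The first gives the primary analysis: "Primary objective will be assessed using two-tailed independent t-tests for comparison between timepoints". The second assigns the same kind of test to every secondary measure and names no contrast. Neither mentions an arm.

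The rest of the document describes a comparison between arms:

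- **Study Design, Hypothesis 1.** The change in femoral condyle shape from 8 weeks to 6 months "will be significantly lower for patients treated with extended-release triamcinolone acetonide than the placebo group".
- **Objectives, Secondary Objectives.** The change in patient-reported outcomes and "a urinary biomarker of cartilage breakdown (uCTXII) between patients treated with extended release triamcinolone acetonide or placebo" is to be compared.
- **Research Procedures, Secondary Objectives.** "Compare the change in patient-reported outcomes between patients treated with extended release triamcinolone acetonide or placebo following ACL reconstruction". The paragraph on urinary CTXII likewise compares the two groups.

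On the data for the primary outcome, Research Procedures, Primary Objective says: "All subjects will undergo MRI examination prior to undergoing the study injection at Visit 3 and again at Visit 4". It also says that the bone area of the medial condyle "has been shown to increase within the first few months after ACL reconstruction". No other section states a test for the primary outcome.

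**The concern.** A comparison of visits estimates how much the knees change on average over time. Hypothesis 1 asks whether they change less on drug than on placebo. The protocol itself expects the medial condyle to enlarge after surgery, so a difference between visits is likely whether or not the drug works.

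The named test is also wrong for the named contrast. The two timepoints are repeat scans of the same people, and an independent-samples t-test ignores that pairing. Pairing the test would cure this second fault but not the first, because the contrast would still be between visits.

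The SAP should fix the primary test before anyone sees the data. Here a reader has to override the one contrast it states. Several analyses then remain open: a t-test on change, a between-arm test at each visit, separate within-arm tests, or ANCOVA. The SAP does not choose among them.

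**Working it through.** **Step 1: the two contrasts side by side.**

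| | Hypothesis 1 | SAP sentence |
|---|---|---|
| Compared | active arm with placebo arm | one timepoint with another |
| Quantity | 8-week to 6-month change | not stated |
| Samples | independent (randomised groups) | dependent (same subjects, Visits 3 and 4) |
| Test named | none | independent t-test |

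The test fits the left-hand column and the contrast fits the right. This conclusion needs no arithmetic.

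**Step 2: inputs for an illustration.** The documents give a total of 30 participants and two randomised groups. They give no alpha, SD, effect size, allocation ratio, dropout or within-subject correlation, so there is no stated figure to reproduce. Assumed: 15 per arm, two-sided alpha 0.05, no dropout, SD of change 1, and correlation r between visits of 0.5 to 0.98. The visit SD is then 1/√(2(1−r)). Two scenarios are used: (A) no drug effect, both arms change by 1; (B) placebo changes by 1 and the drug abolishes the change.

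**Step 3: what each test measures.**

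- *Visit comparison pooled over arms.* The target is the average change: (1+1)/2 = 1 in A and (0+1)/2 = 0.5 in B. It is larger when the drug does nothing.
- *Standard error in the literal unpaired test.* It uses visit SD × √(2/30) = 1/√(30(1−r)). In scenario A the true standard error of the mean change is 1/√30 = 0.183. The test's value is too large by 1/√(1−r): 1.41, 2.24, 3.16, 4.47 and 7.07 times at r = 0.5, 0.8, 0.9, 0.95 and 0.98.
- *Paired version.* The noncentrality is √30 = 5.48 in A and 0.5 × √30 / √(1 + 0.25 × 30/29) = 2.44 in B, against a critical value of 2.05 on 29 df.
- *Between-arm t-test on change.* The target is 0 in A and 1 in B, with standard error √(2/15) = 0.365. The noncentrality is 0 and 2.74 on 28 df, and exact power in B is 75.3%.

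**Step 4: simulated rejection rates** (60,000 trials per cell, bivariate normal visits).

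| Test | Scenario | r=0.5 | 0.8 | 0.9 | 0.95 | 0.98 |
|---|---|---|---|---|---|---|
| Unpaired, visits, pooled | A | 99.5% | 81.9% | 26.6% | 1.2% | 0.0% |
| Unpaired, visits, pooled | B | 40.3% | 5.3% | 0.2% | 0.0% | 0.0% |
| Paired, visits, pooled | A | 100% | 100% | 100% | 100% | 99.9% |
| Paired, visits, pooled | B | 67.0% | 67.3% | 67.6% | 67.3% | 67.3% |
| Between-arm t-test on change | A | 5.1% | 5.0% | 5.1% | 5.0% | 4.9% |
| Between-arm t-test on change | B | 75.4% | 75.5% | 75.5% | 75.0% | 75.1% |
| Between-arm ANCOVA | A | 5.1% | 5.0% | 5.0% | 5.0% | 4.9% |
| Between-arm ANCOVA | B | 84.8% | 78.4% | 75.9% | 74.6% | 73.9% |

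The visit comparisons never reject more often when the drug works than when it does nothing. Only the between-arm tests hold 5% under no drug effect and gain power when there is one.

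**The case against.** **The intent is clear from context.** Hypothesis 1 uses similar language for the change score itself, so the SAP phrase may be shorthand for the change between visits. An independent t-test suits two arms. The trial is randomised and placebo-controlled, and the secondary outcomes are described as between-arm comparisons of change. This stands as a reading of intent: a valid between-arm test was probably meant, and nothing shows that a wrong analysis was planned or run. It does not rescue the text, because no section states that test for the primary outcome and the SAP states a different contrast.

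**The illustration depends on pooling the arms.** The SAP does not say to pool, and its plural could mean one test per arm. On that reading, with no drug effect, each arm's unpaired test rejects in roughly 82–83%, 31%, 5%, 0.2% and 0% of trials at the same values of r. The rates do depend on the reading and on r, so they should not be taken as the size of an error in this trial. But separate tests within each arm do not compare the arms either, so the conclusion is the same.

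**ANCOVA is a preference.** This is largely right. At r of 0.8 or more its power is within about 3 percentage points of the t-test on change, and either is acceptable if named in advance.

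**Conclusion.** The concern holds. Read literally, the only specification of the primary analysis uses the wrong contrast for Hypothesis 1 and applies an unpaired test to repeat measurements. This follows from the text alone and rests on no numerical assumption.

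The practical size cannot be fixed from the documents. Under the assumptions above, whether the literal test rejects far too often or almost never depends on the unstated correlation. The error in the contrast does not: with no drug effect, a correctly paired visit comparison still rejects in about 100% of trials at every r examined, against 5% for a between-arm test.

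The sentence must be corrected before the data are analysed. The fault lies in the specification and is not evidence that the authors intended to ignore the randomised comparison.

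**What to change.** Replace the first SAP sentence with one named test, for example:

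> Total medial femoral condyle volume at Visit 4 (6 months) will be compared between the randomised arms by ANCOVA, adjusting for the Visit 3 (8-week) value, at two-sided alpha 0.05. The between-arm difference will be reported with its 95% confidence interval.

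The smallest edit, an independent t-test between arms on the Visit 3 to Visit 4 change, is equally acceptable if it is the single test named.

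In the same edit:

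- **Primary measure.** Confirm that it is condyle volume. The only calculation described is to "sum the volumes of all slices to generate the total medial condyle volume", but the same section also speaks of bone area, and Hypothesis 1 of shape.
- **Secondary measures.** State the between-arm comparison of change for each. First reconcile the timing: for CTXII, Research Procedures gives a 4-month follow-up and Hypothesis 3 gives 6 months; for patient-reported outcomes, Research Procedures adds 1 and 2 years to the 6 months in Hypothesis 2.
- **Covariates.** Research Procedures, Covariates, says age, sex, race and BMI will be used in the analyses, citing biomarker differences. A plain t-test cannot include them. State which outcomes they apply to and choose the model accordingly.
- **Within-arm comparisons.** Label any comparison of visits within an arm as descriptive, and use a paired test for it.

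The cost is SAP wording only. The Visit 3 and Visit 4 scans are already planned for all subjects, so no new data, visits or participants are needed.

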Patient will provide informed consent prior to undergoing ACL reconstruction with meniscal involvement. At the time of surgery, a knee aspiration will be performed in the operating room after the patient has been anesthetized so that synovial fluid can be collected. Synovial fluid samples will be assessed for the concentration of pro-inflammatory cytokine IL-1alpha. This will be done to identify patients that present with persistent inflammation after injury that may be at increased risk of cartilage degradation. Patients with elevated IL-1alpha, defined as synovial fluid concentrations ≥ 5 pg/mL, will then be randomized to one of two groups. The synovial fluid threshold of 5 pg/mL was based on our previously published study of ACL patients that demonstrated that those with elevated IL-1alpha at the time of surgery less likely to achieve a successful clinical outcome at 2 years (Latttermann et al., Biomed Res Int, 2018).

Eight weeks after surgery, the knee will be aspirated and one group will receive a single 32 mg Zilretta injection and the other group will receive a 5 mL saline injection. The syringes will be blinded to ensure that both the investigator administering the injection and the patient will be blinded to the group assignment. Patients will then be seen again six weeks later. Both prior to injection and at the 6-month follow-up visit, patients will undergo 3T MRI scans so that femoral shape can be assessed and will also be asked to complete patient-reported outcomes questionnaires and provide a urine sample.

Attachments

Subject Recruitment Methods & Advertising

Describe how the study team will identify and recruit subjects. Please consider the following items and provide additional information as needed so that the IRB can follow each step of the recruitment process.

- How will the study team identify potential participants?
- Who will first contact the potential subjects, and how?
- Will you use advertisements? If so, how will you distribute those?
- How and where will the research team meet with potential participants?
- If applicable, describe proposed outreach programs for recruiting women, minorities, or disparate populations.
- How you will minimize undue influence in recruitment?
- Attach copies of all recruiting and advertising materials (emails, verbal scripts, flyers, posts, messages, etc.).

For additional information on recruiting and advertising:

- [IRB Application Instructions - Advertisements](#)

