Biomarker concentrations have been previously shown to differ based on patient age, sex, race, and BMI.⁵⁰ As such, these patient factors will be collected and used as covariates in our statistical analyses.

SAFETY AND OTHER ASSESSMENTS

- Limited Physical examination: Subject height and weight will be monitored, and the injection site will be closely monitored for infection and/or allergic reaction.
- Vital signs: Blood pressure will be assessed per the standard of care
- Radiographic or other imaging assessments: The amount of arthritic changes to the knee will be assessed by the Principal Investigator from each patient's routine standard of care preoperative x-ray. Patients with more than Kellgren Lawrence grade I changes will be excluded from the study. These images will not be reviewed until after the patient has signed a HIPAA-approved informed consent form.
- Assessment of adverse events: Patients that develop AEs/SAEs will be closely monitored until conclusion of the event. For events that are ongoing at the 6-week study visit, we will continue to contact the patient on a monthly basis until the event has resolved or deemed to have reached maximum medical improvement.

All information garnered from safety assessments will be recorded in the patient's medical chart.

Attachments

Data Collection & Research Materials

In this section, please provide the following:

- Describe all sources or methods for obtaining research materials about or from living individuals (such as specimens, records, surveys, interviews, participant observation, etc.), and explain why this information is needed to conduct the study.
- For each source or method described, please list or attach all data to be collected (such as genetic information, interview scripts, survey tools, data collection forms for existing data, etc.).
- If you will conduct a record or chart review, list the beginning and end dates of the records you will view.

Data collection is the responsibility of the clinical trial staff at the site under the supervision of the site investigator. The investigator is responsible for ensuring the accuracy, completeness, legibility, and timeliness of the data reported.

All source documents should be completed in a neat, legible manner to ensure accurate interpretation of data.

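### The SAP's plain t-tests do not match the protocol's covariate commitment (clearest for uCTX-II) and leave the collected pre-injection value unadjusted, a loss of efficiency rather than a bias

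*Combined protocol and SAP*

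**What the plan says.** The SAP is two sentences long. The first assigns the primary objective "two-tailed independent t-tests for comparison between timepoints". The second says that "all secondary measures will be assessed using two-tailed independent t-tests". It names no covariate, no adjustment for the pre-injection value and no analysed variable.

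Under Research Procedures, the Covariates paragraph gives a reason, "Biomarker concentrations have been previously shown to differ based on patient age, sex, race, and BMI", and concludes that "these patient factors will be collected and used as covariates in our statistical analyses".

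The rest of the protocol describes the outcomes as changes compared between arms. In Study Design, Hypothesis 1 concerns the change in femoral condyle shape from 8 weeks to 6 months. Hypothesis 2 concerns "Changes in patient reported-outcomes between eight and 6 months after surgery" and Hypothesis 3 "Changes in a urinary biomarker of cartilage breakdown (uCTXII) between eight and 6 months after surgery", both without a unit after the word eight. The Secondary Objectives text under Research Procedures also compares change between arms for the questionnaires and for uCTX-II.

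The pre-injection measurements exist. Study Design says that, before injection and again at the 6-month visit, patients have an MRI and "will also be asked to complete patient-reported outcomes questionnaires and provide a urine sample". The Background agrees that "the following data will be collected at 8 week and 6 month follow-ups".

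**The concern.** The protocol promises covariates, and the SAP names a test that cannot use them. Nothing says whether an adjusted or an unadjusted result is the main one. If that choice is made after the data are seen, the reported result is open to selection, and with 30 patients the two could differ noticeably.

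The SAP's description of the primary test is also wrong for this design. The two timepoints are paired within each patient, while an independent t-test compares separate groups. The SAP therefore does not itself state the contrast that the hypotheses call for.

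Finally, if change is tested, the pre-injection value enters by subtraction but is not adjusted for. Precision may be given up even though the value is already being collected.

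**Working it through.** **Text.** The covariate sentence covers the team's statistical analyses in general, but the reason given for it concerns biomarker concentrations. uCTX-II is a biomarker and a secondary measure, so both statements apply to it directly. MRI and the questionnaires are covered only if the general wording is taken literally. No other section supplies a covariate model.

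**Inputs.** N = 30, from Study Population and Subject Recruitment. The plan's own derivation is a recruitment yield, 100 enrolled × about 30% = 30, not a power calculation. There are two arms. The allocation ratio is not stated, so 15/15 is assumed; the ratio does not change the relative cost. The documents give no SD or correlation, so two quantities are assumed: r, the pre/post correlation, and k, the follow-up SD divided by the pre-injection SD. The formulas assume a linear pre/post relation with the same slope and SD in both arms, and a roughly normal baseline.

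**Cost of covariates that explain nothing.** Averaged over randomisations, q such terms multiply the variance of the treatment effect by (N − 3)/(N − q − 3).

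- One term, N = 30: 27/26 = 1.038.
- One term, N = 24: 21/20 = 1.05.
- Simulation of 40,000 randomisations at 15/15 with one term: mean 1.038. The factor exceeded 1.04 in about 30% of randomisations, and its 95th percentile was about 1.15.

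**ANCOVA on the pre-injection value against a t-test on change.** The variance ratio is k²(1 − r²)/(1 + k² − 2rk) × 27/26. The first factor cannot exceed 1, because its denominator minus its numerator is (1 − rk)² ≥ 0. So 27/26 is the worst case over every r and k.

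| k | r = 0.5 | r = 0.7 | r = 0.9 |
|---|---|---|---|
| 0.9 | 0.69 | 0.78 | 0.84 |
| 1.0 | 0.78 | 0.88 | 0.99 |
| 1.1 | 0.85 | 0.96 | 1.04 |
| 1.2 | 0.90 | 1.00 | 1.01 |
| 1.3 | 0.95 | 1.03 | 0.95 |

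At k = 1 the ratio is (1 + r)/2 × 27/26: 0.75 × 1.038 = 0.78, 0.85 × 1.038 = 0.88 and 0.95 × 1.038 = 0.99. The change score is the more precise choice there only when (1 + r)/2 exceeds 26/27, that is, r above 25/27 = 0.926.

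**Against a t-test on the follow-up value.** The ratio is (1 − r²) × 27/26: 0.78 at r = 0.5, 0.53 at r = 0.7, and 1.038 at r = 0.

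**Adding age, sex, race and BMI.** With race as one binary term, five terms in all give 27/22. Relative to the pre-injection value alone, this is (27/22)/(27/26) = 26/22 = 1.18. To break even, the four must explain 1 − 22/26 = 0.154 of the residual variance. If race needs several indicators, the cost is higher.

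**Follow-up times, side by side.**

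- Background and Study Design: 8 weeks and 6 months. Study Design also has a return visit six weeks after injection.
- Inclusion Criteria: participation from 8 to 26 weeks after surgery, 26 − 8 = 18 weeks.
- Secondary Objectives: uCTX-II at 4 months after surgery; questionnaires at 6 months, 1 year and 2 years.
- Safety and Other Assessments: adverse events still open at a 6-week visit.
- Costs to Subjects: questionnaires at Visits 3 to 6.

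Eighteen weeks is about 4 months, so the uCTX-II time might have been counted from injection. That is a conjecture for the investigators to confirm.

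**The case against.** The case for leaving the plan alone has four parts.

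*The variable is defined.* A reader might infer that the analysed variable is unknown. The documents do not support that: the SAP points to the primary objective and secondary measures, and Study Design and Research Procedures define these as change compared between arms. What stands is narrower. The SAP's phrase does not describe that contrast, and the primary measure is variously bone shape (Objectives), bone area and bone volume (Primary Objective under Research Procedures).

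*Both statements can be honoured.* A reader might infer that the team cannot follow both. The Covariates paragraph does not say that the factors enter the main test, so an adjusted analysis could sit beside the t-test. This is correct, but the SAP lists no such analysis and does not say which result is the main one.

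*The t-test is valid.* A reader might infer bias from the missing baseline adjustment. Under randomisation a between-arm t-test on change is unbiased, and the hypotheses are framed as change. Adjustment is an efficiency choice, and the table has cells where change scores do slightly better, such as 1.04 at k = 1.1 and r = 0.9. This stands in full.

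*The 4% can be misread.* It is an average over randomisations, so a single trial can lose more. It also covers only the pre-injection term, not the four demographic factors. Both limits stand and belong with the figure.

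**Conclusion.** The mismatch between the Covariates paragraph and the SAP is real. It is clear for uCTX-II and conditional on a broad reading for MRI and patient-reported outcomes. The SAP's wording of the primary contrast needs correcting to match the hypotheses.

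The baseline point concerns precision only. The worst-case expected cost of adjusting is about 4% with 30 patients, or 5% with 24. The possible gain depends on correlations and SDs that the documents do not give. At equal SDs it is about 22% of the variance at r = 0.5, 12% at r = 0.7 and 1% at r = 0.9. No gain for a particular outcome can be derived from the documents, and for the primary it may be small or nil if its pre/post correlation is very high. Nor do the documents settle whether the demographic factors would repay their roughly 18%.

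This should be fixed before the data are analysed. It does not invalidate the trial.

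**What to change.** 1. State in the SAP that each outcome is compared between arms, and name its variable. For the primary, confirm that it is medial femoral condyle volume.
2. Prespecify an ANCOVA for each outcome: follow-up value on arm and pre-injection (Visit 3) value, reporting the adjusted difference with a 95% CI. With the pre-injection value in the model, the arm effect is the same whether the response is the follow-up value or the change, so the hypotheses need no rewording on that account.
3. State in advance whether age, sex, race and BMI enter the main analysis or a sensitivity analysis, and for which outcomes. Make the Covariates paragraph and the SAP agree. Confining them to a uCTX-II sensitivity analysis is one option.
4. Before fixing the list of models, reconcile the follow-up times set out above. Also say whether the serum biomarkers mentioned in the Background are to be analysed.

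The cost is SAP text and a few lines of protocol wording, with no new data. There would be five 6-month models (condyle volume, uCTX-II, IKDC, KOOSglobal, ICOAP), each spending one degree of freedom on the pre-injection value. Six more (three questionnaires × two times) would follow only if the 1- and 2-year assessments are confirmed. A team that prefers change-score t-tests may keep them, but steps 1, 3 and 4 would still be needed.
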